8.1 Endpoint and Other Non-Safety Assessments

Screening and Eligibility Assessment

Screening procedures will be conducted prior to enrollment to determine participant eligibility. The screening process will include:

- A review of inclusion and exclusion criteria to ensure eligibility
- A cognitive assessment using a validated tool (e.g., Mini-Mental State Examination 2 and AD8)
- Informed consent obtained from participants and, if applicable, their legally authorized representative
- A baseline assessment of demographic information and chronic health conditions, Promis-29 measure of physical health, and Lubben social isolation index
- Participants who meet the eligibility criteria will be enrolled in the study.

Baseline Assessments

Prior to the intervention, the following baseline assessments will be completed:

- **Questionnaires:** self-report measures assessing quality of life, mental health, thriving, loneliness, relationship quality, and caregiver guilt (for the adult child only) will be administered.

Intervention Data Collection

Participants will engage in technology sessions, once a week, for four weeks with the following procedures:

- Sessions will be facilitated by trained study personnel between the resident and adult child
- Participants will complete weekly self-reported measures on their session experiences, mood, their study partner's behavior, and perceived benefits
- Study personnel will monitor for potential adverse reactions (e.g., dizziness, discomfort) and document participant responses to the session

Post-Study and Follow-Up Assessments

After the intervention phase is complete, the following assessments will be completed:

- **Interviews:** Interviews will be conducted between the participants and trained study personnel to gather additional information about the participants' experiences and attitude towards the technology. A post-study interview will be conducted with both the resident and adult child participant. A second interview will be conducted with the resident participant at 1-month post intervention.

Questionnaires: self-report measures assessing quality of life, mental health, thriving, loneliness, relationship quality, and caregiver guilt (for the adult child only) will be administered.

8.2 Safety Assessments

SAFETY PLAN

1. Complete Screening Document (Staff at community)
2. MMSE-2 (UCSB/Rendever senior personnel) & AD8 (adult child completes)
3. All proper levels of consent are gathered—consent is also gathered again every time before VR begins if resident has mild or moderate dementia
4. Ask staff to identify three things that might trigger a resident (if he/she has dementia) and three things that typically calm him/her.
5. Train staff on what the VR is like (try on headsets)
6. Who is the clinician/staff member on location that day in the event that there is an adverse reaction? Gather name and phone number/schedules.
7. Senior personnel (grad student, post doc, faculty) will always be operating the VR with the resident if they have dementia.
8. Training with the adult child on VR and how to communicate with parents ahead of time.
9. Trial run with the VR right before it begins to assess how it feels
10. Check in with the resident and adult child throughout the VR sessions.
11. We will also carefully monitor any hallucinations, seizures, or dizzy spells that residents experience by asking staff members if there are any concerns and on what day. If we believe the VR is connected to any hallucinations or seizures, we can discuss the possibility with the family of removing them from the study.

Safety Plan if there is an adverse reaction:

1. Ask to take off their headset and remove it for them.
2. Turn off the sound on the headset and listen to the resident. Try not to persuade them that their feelings aren't real/or are incorrect.
3. Ask how they are feeling and provide comfort.
4. If they are okay, ask if they would still like to continue by viewing the experience from the tablet with their adult child instead of the VR.
5. If they are feeling dizzy, confused, beginning to feel ill, ask if they would like a drink of water or like to lie down.
6. If they are still agitated, remembering the list of things that tend to calm the resident (e.g., taking a walk, a picture, a specific staff member, a specific area that provides comfort)
7. If the researcher is not able to calm the resident, the researcher will ask the staff member on site that day to come over and help calm them.
8. If the adult child is also distressed, the researcher will ask the dementia expert on the grant ([name]) to follow-up with the adult child (if the adult child would like additional information on coping strategies).

8.3 Adverse Events and Serious Adverse Events

8.3.1 Definition of Adverse Events

Any untoward or unfavorable medical occurrence in a human study participant, including any abnormal sign (e.g. abnormal physical exam or laboratory finding), symptom, or disease, temporally associated with the participants' involvement in the research, whether or not considered related to participation in the research.

8.3.2 Definition of Serious Adverse Events

Any adverse event that: (a) results in death, (b) is life threatening, or places the participant at immediate risk of death from the event as it occurred, (c) requires or prolongs hospitalization, (d) causes persistent or significant disability or incapacity, (e) results in congenital anomalies or birth defects, (f) is another condition which investigators judge to represent significant hazards.

8.3.3 Classification of an Adverse Event

8.3.3.1 Severity of Event

Events will be rated as either **mild** (symptoms are easily tolerated and are of minor type causing no loss of time from normal activities; symptoms do not require medical or therapeutic intervention; symptoms are transient), **moderate** (events introduce a low level of inconvenience or concern to the participant and may interfere with daily activities, but are usually improved by simple therapeutic measures; may cause some interference with functioning), or **severe** (events interrupt the participant's normal daily activities and require systemic psychological or medical treatment; usually incapacitating)

8.3.3.2 Relationship to Study Intervention/Experimental Manipulation

All events will be assessed as to the likelihood that they are related to the study intervention and/or participation. Categories are: **definitely related** (the adverse event is clearly related to the investigational procedure), **possibly related** (the adverse event follows a reasonable temporal sequence from administration of the intervention but could readily have been produced by a number of other factors), **not related** (the adverse event is clearly not related to the intervention, another cause is most plausible; and/or a plausible temporal sequence is inconsistent with the onset of the event and the intervention and/or a causal relationship is considered biologically or psychologically implausible).

8.3.3.3 Expectedness

All AEs will be assessed as to whether they were expected to occur or unexpected, meaning not anticipated based on current knowledge found in the protocol and described in study related forms and scripts. Categories are: **unexpected** - nature or severity of the event is not consistent with information about the condition under study or intervention in the protocol, consent form, or recruitment material, or **expected** - event is known to be associated with the intervention or condition under study.

8.3.4 Time Period and Frequency for Event Assessment and Follow-Up

The occurrence of an adverse event (AE) or serious adverse event (SAE) may come to the attention of study personnel during study visits and post-study interviews.

Strict procedures will be followed for collecting and reporting of adverse events and unanticipated problems. All AEs, SAEs, and unanticipated problems (UPs) will be collected on an **Adverse Event Form** in both paper and electronic format. Paper forms will be completed by researchers on site immediately

following the study session in which the event occurred, or immediately after the adverse event comes to their attention (through personal communication from a study participant, family member, or residential community staff). Information on the paper forms will then be transferred to the digital form within 24 hours. PIs ([name] and [name]) will receive an immediate alert whenever an electronic Adverse Event Form is submitted. [name] and [name] will be responsible for classifying adverse events in terms of **severity, expectedness, and potential relatedness** to the study, which will be recorded on the Adverse Event Form.

PIs will record events with start dates occurring any time after informed consent is obtained until the last day of study participation. At each study visit, researchers will carefully monitor for any AEs. AEs will be followed for outcome information until resolution or stabilization.

8.3.5 Adverse Event Reporting

AEs will be reported to PIs within 24 hours. Mild AEs will be reported to the IRB and NIH PO in interim and annual reports. However, moderate or severe AEs will be reported to the IRB and NIH PO within 24 hours of the adverse event occurring or within 24 hours after the adverse event comes to attention via phone or email. Due to the low-risk nature of this project (and safeguards that will be implemented), we anticipate that AEs will be rare and mild. However, if we discover that AEs occur with greater frequency than expected, or are more severe than expected, then we will classify them as UPs, which will trigger expedited reporting and collaboration with IRB and NIH staff. All AEs and UPs will be reported to the NIH PO in quarterly interim reports and in the annual Data and Safety Monitoring Report. The PIs will also report all adverse events and unexpected problems to the IRB in the annual progress report (unless more frequent reporting is requested by the UCSB IRB).

8.3.6 Serious Adverse Event Reporting

SAEs are not anticipated in this study; but, if such an event does occur, it will be reported immediately to the PIs via telephone or email. The PIs will then transmit this information via phone or email to the IRB and the NIH PO within 24 hours. The PIs, along with the IRB and NIH PO, will determine whether the SAE is related to the intervention and which steps (if any) should be taken as a result of the event. The expedited report will be followed by a detailed, written SAE Report as soon as possible, which will be submitted to the IRB and the NIH PO.

8.3.7 Reporting Events to Participants

N/A

8.3.8 Events of Special Interest

N/A

8.3.9 Reporting of Pregnancy

N/A

8.4 Unanticipated Problems

8.4.1 Definition of Unanticipated Problems

This protocol uses the definition of Unanticipated Problems as defined by the Office for Human Research Protections (OHRP). Any incident, experience, or outcome that meets all of the following criteria: (a) unexpected, in terms of the nature, severity, or frequency, given (1) the research procedures that are described in the protocol-related documents, such as the IRB-approved research protocol and informed consent document; and (2) the characteristics of the study population; (b) related or possibly related to participation in the research (possibly related means there is a reasonable possibility that the incident, experience, or outcome may have been caused by the procedures involved in the research); and (c) suggests that the research places participants or other at a greater risk of harm (including physical, psychological, economic, or social harm) than was previously known or recognized.

8.4.2 Unanticipated Problems Reporting

UPs will be reported to PIs within 24 hours. The PIs will then evaluate the severity of the UP and its potential relatedness to the study intervention. They will then transmit this information to the IRB and the NIH PO within 48 hours (via phone or email) to discuss corrective action, if needed. If the UP is classified as related to the study intervention, then the study protocol, and consent procedures and forms, will be modified to incorporate the unanticipated problem and any new safeguards that will be implemented. The expedited report will be followed by a detailed, written UP report as soon as possible. This report will increase a corrective plan and measures to prevent reoccurrence of the UP.

8.4.3 Reporting Unanticipated Problems to Participants

N/A

9 Statistical Considerations

9.1 Statistical Hypotheses

STUDY AIMS:

- **AIM 1:** Determine whether virtual reality (vs. control) improves quality of life for residents and their adult children who live at a distance.
- **AIM 2:** Determine whether the positive effects of virtual reality (vs. control) on quality of life depend upon residents' level of cognitive impairment (MCI vs. mild to moderate AD/ADRD).
- **AIM 3:** Determine whether virtual reality (vs. control) reduces caregiver guilt for adult children and whether these effects depend on the adult child's own responses to the technology and their parent's responses to the technology.

- Primary Efficacy Endpoint(s):
 - Older adults
 - Quality of Life
 - Thriving
 - Positive and negative affectivity
 - Depression
 - Mental health symptoms
 - Loneliness and social connection
 - Relationship quality with adult child
 - Adult Children
 - Thriving
 - Positive and negative affectivity
 - Depression
 - Mental health symptoms
 - Caregiver guilt and perceived stress
 - Relationship quality with parent
- Secondary Efficacy Endpoint(s):
 - Older adults and adult children
 - Conversational, social, and emotional engagement during technology sessions
 - Kinesic (physical) engagement during technology sessions (older adult only)
 - Relationship connection and bonding during technology sessions

9.2 Sample Size Determination

Power analysis approach: The approach to estimating power was to use simulation methods. Using this approach, the hypothesized population model and its associated model parameters are used to randomly generate data for the study, including sampling variability. Data are generated thousands of times, simulating thousands of hypothetical studies, and then summarized to explore how many of the simulated studies contain the parameter of interest. The proportion of time each individual effect is significant across all of the simulations is the power of that effect or the expected number of times one would observe that effect to be significant if an alternative hypothesis was true in the population. This approach is the only way to estimate power in this study because of the complexity of the statistical models needed to estimate the treatment effects, that account for the dyadic relationship (resident-adult child) and the longitudinal repeated measures of the outcomes of interest (7 time points). We used the simulation facilities in Mplus (version 8.3) to estimate the models.

To address the proposed aims, which involve dyadic longitudinal models, some with mediation, the power analysis relied heavily on the Phase 1 pilot data as estimates for effects of interest (including within-group changes in well-being over time, baseline to VR). This helps provide a starting point for the simulated datasets. These models, however, are quite complex and involve model parameters for which the pilot data cannot provide reasonable estimates. For example, the pilot study did not collect data on a control group. To be conservative, the power analysis used conservative estimates of effect sizes for models that included differences between VR and the control group (e.g., $d = 0.2$). To determine power, the analysis focused on power of the treatment impact for a given aim (e.g., the hypothesized increase in

quality of life for those in the VR condition for Aim 1, both concurrently and over time), while varying other model parameters that affect power (e.g., standard error of random intercepts and error variance) and exploring the impact of sample size. That is, simulations considered different sample sizes, variances, and standard errors, to ensure that the planned sample size was a large enough sample to provide sufficient power across all study aims. It is important to note that there are many parameters for which there was no pilot data, so conservative parameter estimates (e.g., moderately large standard errors and small betas) were used for simulation purposes to ensure sufficient power. In many aims, the effect of the treatment includes both concurrent comparisons across VR and the control (Zoom) and longitudinal differences, which were computed using random effects.

Power analysis results: Sample size was determined by a joint consideration of the (a) expected range of effect sizes across the outcome variables, (b) the planned data analytic strategy, and © the expected attrition rate. Because of the complexity of the research design and range of hypotheses to be tested, initial sample size estimates were focused on ensuring a high level of power for detecting effects of the experimental manipulation of VR versus control (Zoom) on the outcomes. Based on pilot data that studied the impact of VR on changes over time in the emotional well-being of resident-adult child dyads (similar to the procedure in the current study), we estimated the range of the parameters from that sample when possible.

The planned sample size needed to detect an effect size corresponds to the smallest of these effect sizes as our minimal detectable effect of interest – a conservative strategy that would give us adequate power. Various simulation studies were run, varying sample size, effect size of concurrent differences and longitudinal differences, and other model characteristics related to power (e.g., error variance and variance of the random effects). While the models for each aim vary in their specific effects, there are similarities across them. The moderating effects of cognitive impairment are the most specific effects, which would lend itself to lower power. Thus, these models were used as a lower bound for power in this grant and guided the decision on sample size, because if these ML-SEM models with moderation had sufficient power, we can be confident that our other proposed analyses would be sufficiently powered.

We specified a ML-SEM model that included a random effects regression model. We modeled the moderation by including an interaction term (4 conditions: treatment group x cognitive impairment) on its prediction of the fixed effect of quality of life for the Resident in T2-T5 and T6-T7. Additionally, we estimated concurrent differences across the four conditions, conservatively estimating that the effect was small across time ($d = .2$). Using parameter constraints, power was studied for concurrent differences between VR and control (e.g., at a given time point) as well as sustained gains over time between VR and Control.

We computed that a sample size of **192 dyads (96 in VR condition, 96 in control)** evenly split between cognitive impairment (**MCI vs. dementia**) will achieve a high level of power (.85) for detecting the minimal expected effect size across the different analytic approaches considered. Assuming an attrition rate of approximately 15% across the 4-month longitudinal study, we calculated a required initial sample size of no less than 181 dyads. Based on this analysis, along with the additional considerations noted above, we selected a slightly higher **initial sample size of 192**. Because data from family dyads is dependent, for most analyses the dyad will be treated as the unit of analysis for assignment to experimental conditions and will be modeled accordingly in all statistical analyses. The results of the simulation study reveal that an effective sample size of 192 dyads will provide high power (85%) for detecting even relatively small effects of the VR condition over control (Zoom), which we conceptualized

to be an effect size of $d=.2$, which affords excellent power for detecting even larger effects, which we anticipate will occur.

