Sample size, recruitment, and statistical power: The resident-adult child dyads (N = 192) will participate from 12 senior living communities (16 dyads per community). Half the communities (n = 6) will be located in central California where the research team from the University of California, Santa Barbara resides. The other half (n = 6) will be in Boston, where the Rendever team resides. A power analysis using simulation methods (for multilevel regression models and structural equation models) was used to determine the sample size. Whenever possible, effect sizes were estimated from the Phase I pilot study data. The attrition rate was assumed to be approximately 15% across the 4- month longitudinal study. The results of the simulation study reveal that a sample size of 192 dyads (96 in VR condition, 96 in control) evenly split between cognitive impairment groups (MCI vs. dementia) will achieve a high level of power (.85) for detecting the minimal expected effect size (conceptualized as effect size of $d=.2$) across the different analytic approaches considered. This sample size will provide high power (85%) for detecting even relatively small effects of the VR condition over control, and excellent power for detecting even larger effects, which are anticipated.

Statistical analysis: Because data from resident-adult child dyads is dependent, and because the dyad is the unit of analysis for assignment to experimental conditions, the analysis of quantitative data will utilize linear models designed for nested (clustered) data. Hypothesis testing will be conducted with multi-level, random effects regression models and multilevel structural equation modeling.

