9.4.2 Analysis of the Primary Endpoint(s)

The longitudinal dataset including survey and observational data will enable both between and within participant tests of the hypotheses outlined. The data collected will have three levels of nestedness: repeated measures over time (Level 1), nested within person (either older adult or adult child; Level 2), nested within intervention group (VR vs. Control; Level 3). For some analyses (e.g., Aim 1 and 2), we would not estimate the dyad together since, for example, we do not have specific hypotheses about how the resident and the adult child will differ from each other over time and because the parent and adult child will complete somewhat different measures. Outcomes related to Aim 1 and Aim2 will be assessed with linear mixed-models and, where appropriate, with multilevel structural equation modeling (ML-SEM). ML-SEM merges traditional multilevel modeling, which can accommodate hierarchical data, with structural equation modeling (SEM) techniques, which can accommodate multiple outcomes and mediators, as well as latent variables. Therefore, the analytic approach for some hypotheses tests (e.g., tests of mediation and tests of dyadic models) will be multilevel structural equation modeling (ML-SEM) in Mplus (or R) to simultaneously estimate a within- and between-person model, accounting for individual change over time and the treatment effect at the between-person level. Using parameter constraints, analyses will examine concurrent differences between VR and control (e.g., at a given time point) as well as sustained gains across VR and control using an approach similar to contrast coding.

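### The 85% power at d=.2 is stated without limit, but a VR-versus-Zoom contrast at a single time point has about 28% power unadjusted, and 36–64% with baseline adjustment at correlations of .5–.8

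*Combined protocol and SAP*

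**What the plan says.** Section 4.1 plans "192 dyads (96 in VR condition, 96 in control) evenly split between cognitive impairment groups" and concludes: "This sample size will provide high power (85%) for detecting even relatively small effects of the VR condition over control". Section 9.2 claims power of .85 "for detecting the minimal expected effect size across the different analytic approaches considered", restates this as 192 dyads that "will provide high power (85%) for detecting even relatively small effects of the VR condition over control (Zoom"), and sets the small effect "to be an effect size of $d=.2$, which affords excellent power for detecting even larger effects".

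On which contrasts are meant, section 9.2 says that "power was studied for concurrent differences between VR and control (e.g., at a given time point"), along with sustained gains. Section 9.4.2 repeats this for the primary analysis: "analyses will examine concurrent differences between VR and control (e.g., at a given time point"), again along with sustained gains. H1a in section 2.1 predicts benefits both concurrently and over time, relative to baseline.

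Section 9.4.2 also says that for Aims 1 and 2 residents and adult children are not modelled jointly, and the moderation model in 9.2 is written for the resident. For losses, 9.2 has "Assuming an attrition rate of approximately 15% across the 4-month longitudinal study". The documents do not give the alpha, the SD behind d, the variance components or correlations in the simulation, or the power reached by each contrast.

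**The concern.** The 85% is attached to VR over Zoom in general, and the text around it names a one-time-point comparison among the contrasts studied. At one time point each resident (or each adult child) supplies one outcome value. A multilevel or structural equation model adds no people to a between-dyad comparison; precision can improve only through correlation with baseline or with other waves. With 96 against 96, an effect of 0.2 SD is only about 1.4 standard errors, well short of what 85% power requires.

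Zoom is the benchmark against which VR's added benefit is judged (section 4.2). A reader who takes the 85% at face value could treat a non-significant result at one time point as evidence against a small VR advantage. Over most of the range below, the design would miss such an effect more often than it found it.

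**Working it through.** **The plan's own figure.** The 85% comes from Mplus simulations and cannot be rerun, because the inputs listed above are missing. The check is therefore a direct calculation for the contrast the plan names.

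**Inputs from the documents.** d = .2; 96 per arm; 15% attrition, so 96 × .85 = 81.6 per arm; residents and adult children analysed separately. Primary outcomes are collected at baseline and three later points (section 6.1.2); section 1.3 schedules some of them, such as quality of life, at all seven post-baseline waves (T2–T8).

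**Assumptions.** Two-sided 5%; d on the between-person SD; one common correlation r between any two waves, shown at .5, .7 and .8; normal approximation.

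**Formulas.**
- Power = Φ(d / √(2V/n) − 1.96), with n per arm.
- V = 1 for one wave, unadjusted.
- V = [1 + (k − 1)r]/k − r² for a baseline-adjusted mean of k post-baseline waves. With k = 1 this is 1 − r².

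**One wave, unadjusted, 96 per arm.** SE = √(2/96) = 0.144; 0.2/0.144 = 1.39; power = Φ(1.39 − 1.96) = 28%. With 81.6 per arm, SE = 0.157 and power = 25%. Unadjusted, 85% would need 2 × (1.96 + 1.036)²/0.2² ≈ 449 per arm.

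**With baseline adjustment** (power at r = .5 / .7 / .8):

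| Contrast | V | 96 per arm | 81.6 per arm |
|---|---|---|---|
| One wave | .75 / .51 / .36 | 36 / 49 / 64% | 31 / 43 / 57% |
| Mean of three waves | .417 / .310 / .227 | 57 / 70 / 83% | 51 / 63 / 77% |
| Mean of seven waves | .321 / .253 / .189 | 69 / 79 / 89% | 62 / 72 / 84% |

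**Correlation needed for 85%.** V must not exceed d²n / [2(1.96 + 1.036)²], which is 0.214 at 96 per arm and 0.182 at 81.6. Solving for r:
- One wave: about .89 (.905 with 15% missing).
- Three waves: about .81 (.85).
- Seven waves: about .76 (.81).

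A correlation near zero would also help an average over many waves (seven waves at r = .1 give 84% at 96 per arm), but repeated scores on the same person are unlikely to be so weakly related.

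**Detectable effect at 85% power**, (1.96 + 1.036) × √(2V/n). Unadjusted, one wave: 0.43 at 96 per arm and 0.47 at 81.6. Baseline-adjusted at r = .7 and 81.6 per arm: 2.996 × √(2 × .51/81.6) ≈ 0.34 for one wave, and 2.996 × √(2 × .31/81.6) ≈ 0.26 for the three-wave mean.

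**Sidedness.** One-sided 5% testing gives 40% unadjusted and 48–75% adjusted for one wave at 96 per arm, still below 85%.

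**The case against.** The strongest reply is that 9.2 never says the single-time-point contrast reached 85%. It says such contrasts were studied, by way of example, in a random-effects structural equation model with phases T2–T5 and T6–T7 and parameter constraints. If those constraints equate effects across waves, a concurrent difference in that model is not a one-wave comparison. This stands as far as it goes: the seven-wave mean reaches 89% at r = .8 with full retention, and a four-wave mean reaches 86%. A reader might infer from the 28% that the simulation was wrong, or that the trial is underpowered for every VR-versus-Zoom contrast. The documents do not support either inference. Equally, 9.2 says its inputs were conservative, and it reports no correlations that would place the design at the favourable end.

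The unadjusted 28% is also not what H1a calls for, since that hypothesis is relative to baseline; the adjusted range is the fairer comparison. The figures at 81.6 per arm are pessimistic, because they remove 15% at every wave used, whereas section 1.2 retains partial data and 9.4.1 uses maximum likelihood.

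Pooling the two dyad members would raise power, but 9.4.2 rules that out for Aims 1 and 2.

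Finally, no rule in the plan treats a null result as excluding d=.2. The risk is one of interpretation.

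**Conclusion.** As a blanket statement, 85% power at d=.2 for VR over Zoom is unsupported. For one time point it holds only if the baseline-outcome correlation is about .89 or more; at .5 to .8, baseline-adjusted power is 36% to 64% with full retention, and 31% to 57% if 15% are missing at that wave. For a time-averaged effect, 85% is attainable when correlations are high: about .76–.81 or more with full retention, and about .81–.85 with 15% missing throughout, the lower ends applying to seven waves and the upper to three.

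This rests on two-sided 5%, d on the between-person SD, equal correlations between waves and, for the single-wave figures, no borrowing from other post-baseline waves. Over r = 0 to .9 single-wave power at 96 per arm runs from 28% to 89%, so the missing correlation is decisive. No multiplicity adjustment is included; any applied under 9.4.1 would lower these figures.

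**What to change.** In sections 4.1 and 9.2:
- Remove the unqualified 85% at d=.2.
- State the alpha and sidedness, the SD behind d, and the correlations or variance components used in the simulation.
- Report power or detectable effect separately for the single-time-point contrast and the sustained (time-averaged) contrast, with attrition included. At 85% power, r = .7 and 15% attrition, for example, these are d of about 0.34 for one wave and 0.26 for the three-wave average.
- State that a non-significant single-time-point result does not rule out d=.2.

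The correction should not be used to name a new main contrast. Section 1.2 already reports final attrition totals, so that choice would appear to come after data collection.

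The cost is wording in two sections and one re-run of the existing simulation, with no added participants or visits. The downside is that the stated sensitivity becomes less favourable.
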